### **6.5.1 Dosing Windows**

During Cycles 1 and 2:

- Participants may be dosed with ipilimumab 3 mg/kg and nivolumab 1 mg/kg with no less than 19 days between
  - C1D1 and C1D21
  - C1D21 and C2D1
  - C2D1 and C2D21
  - C2D21 and C3D1

During Cycle 3 and beyond:

- Participants may be dosed no less than 27 days from the previous dose of drug

Participants may be dosed up to 3 business days after the scheduled date if necessary, or longer in the event of a toxicity requiring dose delay. Subsequent dosing should be based on the actual date of administration of the previous dose of drug. Treatment compliance will be monitored by drug accountability as well as the participant's medical record and eCRF.

### **6.5.2 Study Medications**

Nivolumab 1 mg/kg (30 min IV infusion) and ipilimumab 3 mg/kg (90 minute IV infusion) will be administered every 3 weeks for 4 doses, followed by nivolumab 480 mg every 4 weeks. The rationale for this dose schedule is provided in Section 1.1.7. The schedule of investigational treatments is divided into two 42-day cycles at the start of therapy, followed by ongoing 4-week cycles. This dosing schedule is described in detail in Table 6.5-1.

Refer to the Pharmacy Information sheets for more detail. There are no pre-medications recommended on the first cycle. If an acute infusion reaction is noted, participants should be managed according to Section 6.5.6. See Section 6.5.4 for information on Management Algorithms for Immuno-Oncology Agents.

### **6.5.3 Dose Modifications and Delays**

#### **6.5.3.1 Dose Modifications**

Dose reductions and discontinuation of ipilimumab or nivolumab for the management of toxicities of individual participants are permitted at the discretion of the treating physician. Dose escalations are not permitted.

### **6.5.3.2 Dose Delays**

Dose delay criteria apply for all drug-related adverse events (regardless of whether or not the event is attributed to nivolumab, ipilimumab, or both).

Study therapy administration should be delayed for the following:

- Any Grade  $\geq 2$  non-skin, drug-related adverse event, with the following exceptions:
  - Grade 2 drug-related fatigue or laboratory abnormalities do not require a treatment delay
- Any Grade 3 skin, drug-related adverse event
- Any Grade 3, drug-related laboratory abnormality, with the following exceptions for asymptomatic amylase or lipase, AST, ALT, or total bilirubin:
  - Grade 3 amylase or lipase abnormalities that are not associated with symptoms or clinical manifestations of pancreatitis do not require a dose delay
  - If a participant has a baseline AST, ALT, or total bilirubin that is within normal limits, delay dosing for drug-related Grade  $\geq 2$  toxicity
  - If a participant has baseline AST, ALT, or total bilirubin within the Grade 1 toxicity range, delay dosing for drug-related Grade  $\geq 3$  toxicity
- Any adverse event, laboratory abnormality, or intercurrent illness that, in the judgment of the investigator, warrants delaying the dose of study medication

### **6.5.3.3 Criteria to Resume Treatment**

Participants may resume treatment with study therapy when the drug-related AE(s) resolve to Grade  $\leq 1$  or baseline value, with the following exceptions:

- Participants may resume treatment in the presence of Grade 2 fatigue
- Participants with baseline Grade 1 AST/ALT or total bilirubin who require dose delays for reasons other than a 2-grade shift in AST/ALT or total bilirubin may resume treatment in the presence of Grade 2 AST/ALT OR total bilirubin
- Drug-related pulmonary toxicity must have resolved to baseline before treatment is resumed
- Drug-related endocrinopathies adequately controlled with only physiologic hormone replacement may resume treatment

If the criteria to resume treatment are met, the participant should restart treatment at the next scheduled timepoint per protocol. Doses should not be skipped.

If treatment is delayed  $> 6$  weeks (42 days) from the last dose due to drug-related toxicity, the participant must be permanently discontinued from study therapy, except as specified in Section 6.5.3.4. In the event treatment is

delayed > 6 weeks due to reasons other than study drug-related toxicity, the case should be discussed with the Principal Investigator before proceeding.

#### **6.5.3.4 Discontinuation Criteria**

Treatment with study therapy should be permanently discontinued for the following:

- Any Grade 2 drug-related uveitis or eye pain or blurred vision that does not respond to topical therapy and does not improve to Grade 1 severity within the re-treatment period OR requires systemic treatment
- Any Grade 3 non-skin, drug-related AE lasting > 7 days, with the following exceptions:
  - Grade 3 drug-related uveitis, pneumonitis, bronchospasm, neurologic toxicity, hypersensitivity reaction, or infusion reaction of any duration requires discontinuation
  - Grade 3 drug-related laboratory abnormalities do not require treatment discontinuation except:
    - ◆ Grade 3 drug-related thrombocytopenia > 7 days or associated with bleeding requires discontinuation
    - ◆ Any drug-related liver function test (LFT) abnormality that meets the following criteria require discontinuation:
      - AST or ALT > 8 x ULN
      - Total bilirubin > 5 x ULN
      - Concurrent AST or ALT > 3 x ULN and total bilirubin > 2 x ULN
- Any Grade 4 drug-related AE or laboratory abnormality, except for the following events which do not require discontinuation:
  - Grade 4 neutropenia  $\leq$  7 days
  - Grade 4 lymphopenia or leukopenia
  - Isolated Grade 4 electrolyte imbalances/abnormalities that are not associated with clinical sequelae and are corrected with supplementation/appropriate management within 72 hours of their onset
  - Grade 4 amylase or lipase abnormalities that are not associated with symptoms or clinical manifestations, or radiographic signs of pancreatitis. It is recommended to consult with the Principal Investigator for Grade 4 amylase or lipase abnormalities
  - For Grade 4 endocrinopathy AEs such as adrenal insufficiency, ACTH deficiency, hyper or hypothyroidosis, or glucose intolerance, which resolve or are adequately controlled with physiologic hormone replacement (steroids, thyroid hormones) or glucose controlling agents, respectively, retreatment can be considered after discussion with the Principal Investigator
- Any dosing interruption lasting > 6 weeks from the last dose with the following exceptions:

- Dosing interruptions to allow for prolonged steroid tapers to manage drug-related AEs are allowed. Prior to re-initiating treatment in a participant with a dosing interruption lasting > 6 weeks from the last dose, the Principal Investigator must be consulted
- Dosing interruptions > 6 weeks from the last dose that occur for non-drug-related reasons may be allowed if approved by the Principal Investigator
- Any AE, laboratory abnormality, or intercurrent illness which, in the judgment of the Investigator, presents a substantial clinical risk to the participant with continued study therapy dosing

Tumor assessments for all participants should continue as per protocol even if study therapy dosing is interrupted.

#### **6.5.4 Management Algorithms for Immuno-Oncology Agents**

Immuno-oncology agents are associated with AEs that can differ in severity and duration from AEs caused by other therapeutic classes. Nivolumab and ipilimumab are considered immuno-oncology agents in this protocol. Early recognition and management of AEs associated with immuno-oncology agents may mitigate severe toxicity. Management algorithms have been developed to assist investigators in assessing and managing the following groups of AEs:

- Gastrointestinal
- Renal
- Pulmonary
- Hepatic
- Endocrinopathies
- Skin
- Neurological

The recommendation is to follow the nivolumab algorithms for immune-oncology agents (I-O) in order to standardize the safety management across the study.

The algorithms are found in the Nivolumab Investigator Brochure and Appendix 2 of this protocol.

#### **6.5.5 Treatment Beyond Disease Progression**

Accumulating evidence indicates a minority of participants treated with immunotherapy may derive clinical benefit despite initial evidence of progressive disease (PD)[48]. The assessment of clinical benefit should be balanced by clinical judgment as to whether the participant is clinically deteriorating and unlikely to receive any

benefit from continued study therapy. Participants will be permitted to continue treatment beyond initial progressive disease as long as all of the following criteria are met and clearly documented:

- Investigator-assessed clinical benefit and no rapid disease progression;
- Tolerating study drug(s);
- Stable performance status;
- Treatment beyond progression will not delay an imminent intervention to prevent serious complications of disease progression
- Participant provides written informed consent prior to receiving additional study therapy, using an ICF describing any reasonably foreseeable risks or discomforts, or other alternative treatment options

Additionally, patients who have progressed between screening imaging and baseline imaging (See Table 7.4-1) but prior to initiation of ipilimumab/nivolumab may be allowed to proceed with ipilimumab/nivolumab beyond progression at the investigator's discretion. All decisions to continue treatment beyond initial progression must be discussed with the Principal Investigator and documented in the study records. The participant will continue to receive monitoring according to the Time and Events Schedules in Table 7.1-2 and Table 7.1-3. A radiographic assessment should be performed within 6 weeks of original PD to determine whether there has been a decrease in the tumor size, or continued PD. For the participants who continue study therapy beyond PD, further progression is defined as an additional 10% increase in tumor burden from time of initial PD. This includes an increase in the sum of all target lesions and/or the development of new measurable lesions. For patients with evaluable disease only, further progression is defined as unequivocal disease progression of non-target lesions or the development of new lesions from time of initial PD. Treatment should be discontinued permanently upon documentation of further disease progression. New lesions are considered measurable at the time of initial progression if the longest diameter is at least 10 mm (except for pathological lymph nodes, which must have a short axis of at least 15 mm). Any new lesion considered non-measurable at the time of initial progression may become measurable and therefore included in the tumor burden measurement if the longest diameter increases to at least 10 mm (except for pathological lymph nodes, which must have an increase in short axis to at least 15 mm).

For statistical analyses that include the investigator-assessed progression date, participants who continue treatment beyond initial investigator-assessed, RECIST 1.1-defined progression will be considered to have investigator-assessed progressive disease at the time of the initial progression event. For participants in all treatment arms, global deterioration of health status requiring discontinuation of treatment without objective evidence of disease progression at that time should be reported as 'symptomatic deterioration'. Every effort should be made to document objective progression (i.e., radiographic confirmation) even after discontinuation of treatment.

## **6.5.6 Treatment of Nivolumab- or Ipilimumab-Related Infusion Reactions**

Because nivolumab and ipilimumab contain only human immunoglobulin protein sequences, they are unlikely to be immunogenic and induce infusion or hypersensitivity reactions. However, if such a reaction were to occur,

it might manifest with fever, chills, rigors, headache, rash, pruritus, arthralgias, hypo or hypertension, bronchospasm, or other symptoms. All Grade 3 or 4 infusion reactions should be reported within 24 hours to the Principal Investigator and reported as a serious adverse event (SAE) if criteria are met. Infusion reactions should be graded according to NCI CTCAE (version 4.0) guidelines. Treatment recommendations are provided below and may be modified based on local treatment standards and guidelines as appropriate:

**For Grade 1 symptoms:** (Mild reaction; infusion interruption not indicated; intervention not indicated)

- Remain at bedside and monitor participant until recovery from symptoms. The following prophylactic premedications are recommended for future infusions: diphenhydramine 50 mg (or equivalent) and/or paracetamol 325 to 1000 mg (acetaminophen) at least 30 minutes before additional study therapy administrations

**For Grade 2 symptoms:** (Moderate reaction requires therapy or infusion interruption but responds promptly to symptomatic treatment [eg, antihistamines, non-steroidal anti-inflammatory drugs, narcotics, corticosteroids, bronchodilators, IV fluids]; prophylactic medications indicated for  $\leq$  24 hours).

- Stop the study therapy infusion, begin an IV infusion of normal saline, and treat the participant with diphenhydramine 50 mg IV (or equivalent) and/or paracetamol 325 to 1000 mg (acetaminophen); remain at bedside and monitor the participant until resolution of symptoms. Corticosteroid or bronchodilator therapy may also be administered as appropriate. If the infusion is interrupted, then restart the infusion at 50% of the original infusion rate when symptoms resolve; if no further complications ensue after 30 minutes, the rate may be increased to 100% of the original infusion rate. Monitor participant closely. If symptoms recur then no further study therapy will be administered at that visit. Administer diphenhydramine 50 mg IV, and remain at bedside and monitor the participant until resolution of symptoms. The amount of study drug infused must be recorded on the case report form (CRF).
- The following prophylactic premedications are recommended for future infusions:

diphenhydramine 50 mg (or equivalent) and/or paracetamol 325 to 1000 mg (acetaminophen) should be administered at least 30 minutes before additional study therapy administrations. If necessary, corticosteroids (recommended dose: up to 25 mg of IV hydrocortisone or equivalent) may be used.

**For Grade 3 or Grade 4 symptoms:** (severe reaction, Grade 3: prolonged [ie, not rapidly responsive to symptomatic medication and/or brief interruption of infusion]; recurrence of symptoms following initial improvement; hospitalization indicated for other clinical sequelae [eg, renal impairment, pulmonary infiltrates]). Grade 4: (life threatening; pressor or ventilator support indicated).

Immediately discontinue infusion of study therapy. Begin an IV infusion of normal saline and treat the participant as follows. Recommend bronchodilators, epinephrine 0.2 to 1 mg of a 1:1,000 solution for subcutaneous administration or 0.1 to 0.25 mg of a 1:10,000 solution injected slowly for IV administration, and/or diphenhydramine 50 mg IV with methylprednisolone 100 mg IV (or equivalent), as needed. Participants should be monitored until the investigator is comfortable that the symptoms will not recur. Study therapy will

be permanently discontinued. Investigators should follow their institutional guidelines for the treatment of anaphylaxis. Remain at bedside and monitor participant until recovery from symptoms.

In the case of late-occurring hypersensitivity symptoms (eg, appearance of a localized or generalized pruritus within 1 week after treatment), symptomatic treatment may be given (eg, oral antihistamine, or corticosteroids)

## **6.6 Treatment Compliance**

Treatment compliance will be monitored by drug accountability as well as the participant's medical record and CRF.

## **6.7 Destruction or Return of Investigational Product**

For this study, IP (those supplied by BMS, a vendor or sourced by the investigator) such as partially used study drug containers, vials and syringes may be destroyed on site.

It is the investigator's or designee's responsibility to arrange for disposal, provided that procedures for proper disposal have been established according to applicable federal, state, local and institutional guidelines and procedures and provided that appropriate records of disposal are kept. The following minimal standards must be met:

- On-site disposal practices must not expose humans to risks from the drug
- Written procedures for on-site disposal are available and followed. The procedures must be filed with the site's SOPs and a copy provided to BMS upon request
- Records are maintained that allow for traceability of each container, including the date disposed of, quantity disposed, and identification of the person disposing the containers. The method of disposal, ie, incinerator, licensed sanitary landfill, or licensed waste disposal vendor must be documented
- Accountability and disposal records are complete, up-to-date, and available for the Monitor to review throughout the clinical trial period

It is the investigator's or designee's responsibility to arrange for disposal of all empty containers. If conditions for destruction cannot be met the responsible Study Monitor will make arrangements for return of IP provided by BMS (or its vendors). Destruction of non-IP sourced by the site, not supplied by BMS, is solely the responsibility of the investigator or designee.

Please refer to Section 10.2.2 for guidance on IP records and documentation.

## 7 STUDY ASSESSMENTS AND PROCEDURES

### 7.1 Flow Chart/Time and Event Schedule

**Table 7.1-1.** Screening Procedural Outline (MCC 18914)A

Procedure	Screening	Notes
Informed Consent	X	Informed Consent may be obtained at any time, provided it is prior to conduct of any study-related procedures. Note that SAEs are collected from the date of consent.
Inclusion/Exclusion Criteria	X	All inclusion/exclusion criteria should be assessed at screening and confirmed prior to study initiation.
Medical History	X	
Prior Systemic Therapy	X	
Safety Assessments		
Physical Examination	X	
Physical Measurements	X	Include Height, Weight, and ECOG performance Status. Within 28 days prior to thoracic RT.
Vital Signs and Oxygen saturation	X	Temperature, BP, HR, and O 2 saturation at rest by pulse oximetry. Obtain vital signs at the screening visit and within 72 hours prior to thoracic RT.
Assessment of Signs and Symptoms	X	Within 28 days prior to initiation of thoracic RT.
Concomitant Medication Collection	X	Within 28 days prior to initiation of Thoracic RT.
Laboratory Tests	X	CBC with differential, chemistry panel including LDH, AST, ALT, ALP, T.Bili, BUN or serum urea level, uric acid, creatinine, Ca, Mg, Na, K, Cl, P, glucose, bicarbonates (optional), albumin, amylase, lipase, TSH (reflex to free T 3 , free T 4 for abnormal TSH result), hepatitis B surface antigen (HBV sAg), and hepatitis C antibody (HCV Ab) within 28 days prior to initiation of thoracic RT. Screening labs done within 72 hours prior to first dose can also be used for on treatment lab purposes at Day 1 dosing.
ECG	X	Within 28 days prior to initiation of thoracic RT.

Pregnancy Test	X	Performed within 24 hours prior to initiation of thoracic RT for WOCBP only (serum or urine - local/site).
Efficacy/Biomarker Assessments		
Radiographic Tumor Assessment	X	Within 28 days prior to initiation of Thoracic RT. ---CT/ Chest-With IV contrast preferred. ---CT/MRI Abdomen-With oral and IV contrast preferred. ---CT/MRI Pelvis-With oral and IV contrast preferred. Only required if patient has known pelvic visceral metastases or bony metastases in the pelvis. ---MRI/CT Brain-with contrast if possible. MRI preferred.
Attempt collection of tumor tissue for pathologic confirmation and exploratory biomarker evaluation	X	Although it is not required, a serious attempt must be made to obtain diagnostic tumor tissue for confirmation of small cell pathologic diagnosis and for exploratory endpoints. (FFPE) tumor tissue block or minimum of 10 slides, obtained from core biopsy, punch biopsy, excisional biopsy or surgical specimen). Fine needle aspiration is sufficient if that is the only available tissue. Archival tumor material must be made available.
Moffitt Cancer Research Network/Clinical Drug Supplies		
Phone calls to MCRN		Phone calls must be made to MCRN as follows:  Screening phone call to IVRS: For participant number assignment at the time informed consent is obtained.

A-Screening Procedure Visit cannot be more than 28 days before initiation of RT

**Table 7.1-2. On-Treatment Assessments for All Participants, Thoracic Radiation TherapyA,B**

Procedure	Radiation Treatments 1-5	Radiation Treatments 6-10	Notes
	Beginning of Week 1	End of Week 2	
Targeted Physical Examination	X	X	Within 72 hours prior to initiating (Week 1) and after ending (Week 2) thoracic radiation therapy.
Vital Signs and Oxygen Saturation	X	X	Temperature, BP, HR, O 2 saturation at rest by pulse oximetry at rest (also monitor amount of supplemental oxygen if applicable) within 72 hours prior to initiating and after ending Thoracic Radiation Therapy and at any time a participant has any new or worsening respiratory symptoms. These can also be used for screening purposes if appropriate.
Physical Measurements	X	X	Includes Weight and ECOG performance status within 72 hours prior to dosing. These can also be used for screening purposes if appropriate.
Adverse Events Assessment	CONTINUOUS		Assessed using NCI CTCAE v. 4.0. SAEs should be reported within 24 hours through the MCRN protocol outlined in Section 8.1.
Review of Concomitant Medications	X	X	
Extended Laboratory Tests	X	X	Extended on-study local laboratory assessments should be done within 72 hours prior to initiation of thoracic RT (Week 1) and within 72 hours of completing thoracic RT (Week 2). Labs to be collected include CBC with differential, uric acid, BUN or serum urea level, creatinine, Na, K, Ca, Mg, phosphorus, chloride, bicarbonate (optional), amylase, lipase, glucose, AST, ALT, total bilirubin, alkaline phosphatase, LDH.

Thyroid Function Testing	X		TSH (reflex to free T3 and free T4 if abnormal result) to be performed every 6 weeks (+/-1 week) throughout the study.
Pregnancy Test	X		Serum or urine within 24 hours prior to first dose and then at least once every 4 weeks regardless of dosing schedule.
Efficacy Assessments			
Radiographic Tumor Assessment		NA	See Table 7.4-1 and Table 7.4-2 for CT and MRI scan schedule.
Additional Exploratory Biomarker Testing			
Serum, Whole Blood Collection	X	X	See Table 7.5-1 for biomarker sampling schedule.

A Thoracic RT start must be at least 3 weeks but not more than 8 weeks after completion of platinum based chemotherapy
 
BPlease see section 5.2 for details of RT treatment schedule
			

**Table 7.1-3.** On-Treatment Assessments for All Participants, Combined Nivolumab and Ipilimumab (Cycle 1 [cycle length = 42 days])A

Procedure	Cycles 1 and 2		Notes
	Day 1	Day 22	
Targeted Physical Examination	X	X	Within 72 hours prior to dosing.
Vital Signs and Oxygen Saturation	X	X	Temperature, BP, HR, O 2 saturation at rest by pulse oximetry at rest (also monitor amount of supplemental oxygen if applicable) within 72 hours prior to dosing and at any time a participant has any new or worsening respiratory symptoms.
Physical Measurements	X	X	Includes Weight and ECOG performance status within 72 hours prior to dosing.
Adverse Events Assessment	CONTINUOUS		Assessed using NCI CTCAE v. 4.0. SAEs should be reported within 24 hours through the MCRN protocol outlined in Section 8.1.

Review of Concomitant Medications	X	X	
Extended Laboratory Tests	X	X	Extended on-study local laboratory assessments should be done within 72 hours prior to dosing on Days 1, 22 and include: CBC with differential, uric acid, BUN or serum urea level, creatinine, Na, K, Ca, Mg, phosphorus, chloride, bicarbonate (optional), amylase, lipase, glucose, AST, ALT, total bilirubin, alkaline phosphatase, LDH.
Thyroid Function Testing	X		TSH (reflex to free T3 and free T4 if abnormal result) to be performed every 6 weeks (+/- 1 week). (Day 1 of each Cycle).
Pregnancy Test	X	X	Serum or urine within 24 hours prior to first dose and then at least once every 4 weeks regardless of dosing schedule.
Efficacy Assessments			
			CT chest, CT/MRI abdomen, and any other known or suspected sites of disease. Repeat CT/MRI of pelvis is required for participants with pelvic metastases at baseline, or if clinically indicated. Participants should have surveillance MRI/CT scans of the brain every 12 weeks or sooner if clinically indicated.
Radiographic Tumor Assessment		See Note	See Table 7.4-1 and Table 7.4-2 for CT and MRI scan schedule.
Additional Exploratory Biomarker Testing			
Serum, Whole Blood, Tumor Biopsy	X	X	See Table 7.5-1 for biomarker sampling schedule.
Clinical Drug Supplies			
Administer Ipi-3/Nivo-1	X	X	

ACycle 1 must start at least 14 days but not more than 21 days after completion of RT

B Please see section 6.5.1 for Dosing Windows

**Table 7.1-4.** On-Treatment Assessments for All Participants, Cycle 3 and Subsequent cycles (cycle 3+ length = 28 days)A,B

Procedure	Cycle 3+ Day 1	Notes
Targeted Physical Examination	X	Within 72 hours prior to dosing.
Vital Signs and Oxygen Saturation	X	Temperature, BP, HR, O 2 saturation at rest by pulse oximetry at rest (also monitor amount of supplemental oxygen if applicable) within 72 hours prior to dosing and at any time a participant has any new or worsening respiratory symptoms.
Physical Measurements	X	Includes Weight and ECOG performance status within 72 hours prior to dosing.
Adverse Events Assessment	CONTINUOUS	Assessed using NCI CTCAE v. 4.0. SAEs should be reported within 24 hours through the MCRN protocol outlined in Section 8.1.
Review of Concomitant Medications	X	
Extended Laboratory Tests	X	Extended on-study local laboratory assessments should be done within 72 hours prior to dosing for Cycle 3 and every cycle thereafter and include: CBC with differential, uric acid, BUN or serum urea level, creatinine, Na, K, Ca, Mg, phosphorus, chloride, bicarbonate (optional), amylase, lipase, glucose, AST, ALT, total bilirubin, alkaline phosphatase, LDH.
Thyroid Function Testing	X (every 2 cycles)	TSH (reflex to free T3 and free T4 if abnormal result) to be performed every 6 weeks (+/- 1 week)
Pregnancy Test	X (every 2 cycles)	Serum or urine within 24 hours prior to first dose and then at least once every 4 weeks regardless of dosing schedule.
Efficacy Assessments		
Radiographic Tumor Assessment	See Note	CT chest, CT/MRI abdomen, and any other known or suspected sites of disease. Repeat CT/MRI of pelvis is required for participants with pelvic metastases at baseline, or if clinically indicated. See Table 7.4-1 and Table 7.4-2 for CT and MRI scan schedule.
Additional Exploratory		

Biomarker Testing		
Serum, Whole Blood, Tumor Biopsy	See Note	See Table 7.5-1 for biomarker sampling schedule.
Clinical Drug Supplies		
Administer Nivo 480mg	X	

ACycle 3 must start at least 42 days but not more than 56 days after completion of Cycle 1 and 2

B Please see section 6.5.1 for Dosing Windows

**Table 7.1-5.** Follow-Up Assessments for All Participants (MCC 18914)

Procedure	Follow-Up Visits 1 and 2A	Survival Follow-Up VisitsB	Notes
Safety Assessments			
Targeted Physical Examination	X		To assess for potential late emergent study drug-related issues.
Adverse Events Assessment	X	X	NSAEs and SAEs must be collected up to 30 days after study drug discontinuation. SAEs that relate to any later protocol specified procedure must be collected. SAEs should be reported through the MCRN protocol outlined in Section 8.1.
Review of Concomitant Medications	X	X	
Extended Laboratory Tests	X		CBC with differential, uric acid, BUN or serum urea level, creatinine, Na, K, Ca, Mg, phosphorus, chloride, bicarbonate (optional), amylase, lipase, glucose, AST, ALT, total bilirubin, alkaline phosphatase, LDH.
Thyroid Function Testing	X		TSH (reflex to free T3 and free T4 if abnormal result).
Pregnancy Test	X		Serum or urine.

Efficacy Assessments			
Radiographic Tumor Assessment	See Note	See Note	See Table 7.4-1 and Table 7.4-2 for CT and MRI scan schedule.
Exploratory Biomarker Testing			
Serum, Whole Blood, Tumor Biopsy	See Note		See Table 7.5-1 for biomarker sampling schedule.
Participant Status			
Survival Status	X	X	Every 3 months after follow-up visit 2; may be accomplished by visit or phone contact, to update survival information and assess subsequent anti-cancer therapy.

A-Follow-up visits occur as follows: X01 = 35 days  $\pm$  7 days from last dose, X02 = 80 days  $\pm$  7 days from X01

B-Survival visits continue every 3 months  $\pm$  14 days after Follow-up Visit 2 until death, lost to follow-up, or withdrawal of study consent

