#### HIGHLY EFFECTIVE METHODS OF CONTRACEPTION

At a minimum, participants must agree to the use of one highly effective method of contraception as listed below:

Highly effective methods of contraception have a failure rate of < 1% when used consistently and correctly. WOCBP participants and female partners of male participants who are WOCBP are expected to use one of the highly effective methods of contraception listed below. Male participants must inform their female partners who are WOCBP of the contraceptive requirements of the protocol and are expected to adhere to using contraception with their partner. Contraception methods are as follows:

- Progestogen-only hormonal contraception associated with inhibition of ovulation.
- Hormonal methods of contraception, including oral contraceptive pills containing combined estrogen + progesterone, vaginal ring, injectables, implants, and intrauterine devices (IUDs) such as Mirena®
- Nonhormonal IUDs, such as ParaGard®
- Bilateral tubal occlusion

- Vasectomized partner with documented azoospermia 90 days after procedure
  - Vasectomized partner is a highly effective birth control method provided that partner is the sole sexual partner of the WOCBP trial participant and that the vasectomized partner has received medical assessment of the surgical success.
- Intrauterine hormone-releasing system (IUS)
- Complete abstinence
  - Complete abstinence is defined as the complete avoidance of heterosexual intercourse
  - Complete abstinence is an acceptable form of contraception for all study drugs and must be used throughout the duration of the study treatment (plus 5 half-lives of the investigational drug plus 30 days);
  - It is not necessary to use any other method of contraception when complete abstinence is elected;
  - Participants who choose complete abstinence must continue to have pregnancy tests, as specified in Section 7.
  - Acceptable alternate methods of highly effective contraception must be discussed in the event that the participant chooses to forego complete abstinence.
  - The reliability of sexual abstinence needs to be evaluated in relation to the duration of the clinical trial and the preferred and usual lifestyle of the participant.

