F See Table 7.1-4 for detailed instructions related to ongoing assessments with nivolumab maintenance therapy

G See Table 7.1-5 for details of follow up after discontinuation of study therapy.

H See Table 7.1-5 for details of survival follow up visits.

K Required only if patient has known history of pelvic metastases

L CT brain w/ contrast acceptable

M For exploratory biomarker evaluation (prefer surgical specimen or core biopsy tissue, FNA also acceptable)

N See Table 7.5-1 for details of peripheral blood collection for biomarkers

O Anytime within 28 days before initiation of RT

[figure not shown]
P Must start more than 14 days but less than 28 days after completion of RT

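### Table 7.1-4 marks maintenance pregnancy and thyroid tests every 56 days, a longer interval than the notes in the same rows allow

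*Combined protocol and SAP*

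**What the plan says.** Table 7.1-4 of the protocol sets the on-treatment assessments for nivolumab maintenance. Its title fixes the cycle length: "Cycle 3 and Subsequent cycles (cycle 3+ length = 28 days". It has one visit column, Day 1 of each cycle.

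- In both the thyroid row and the pregnancy row the cell reads "X (every 2 cycles" (the closing bracket is left off here).
- The pregnancy note in that row reads "Serum or urine within 24 hours prior to first dose and then at least once every 4 weeks regardless of dosing schedule".
- The thyroid note in that row reads "TSH (reflex to free T3 and free T4 if abnormal result) to be performed every 6 weeks (+/- 1 week" (closing bracket again left off).

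Related text elsewhere:

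- Table 7.1-2 carries both notes and extends the 6-week TSH rule to the whole study.
- Table 7.1-3, for Cycles 1 and 2, has the same pregnancy note and ties TSH to the start of each cycle: "to be performed every 6 weeks (+/- 1 week). (Day 1 of each Cycle".
- Section 6.5.1 sets the shortest dosing interval from Cycle 3 on: "Participants may be dosed no less than 27 days from the previous dose of drug".
- The weekly columns of the Appendix 1 calendar stop at Week 27. Its footnote F sends sites back to the table: "See Table 7.1-4 for detailed instructions related to ongoing assessments with nivolumab maintenance therapy".
- The contraception text in Section 4.4.1 also relies on Section 7: "Participants who choose complete abstinence must continue to have pregnancy tests, as specified in Section 7".

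No text says whether the cell or the note prevails when they differ.

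**The concern.** Site staff usually build visit schedules from the grid and read the notes for detail. Here the grid gives a longer interval than the notes in the same two rows.

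The pregnancy row matters more. Nivolumab is given every cycle, so a site working from the cell would give every second maintenance dose to a woman of childbearing potential with no test in that cycle. Sections 4.6 and 8.4 require immediate notification of a pregnancy and, in most cases, permanent discontinuation of study drug. Later detection could therefore mean a dose that would otherwise have been withheld.

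The thyroid row is secondary. Section 1.1.3 lists hypothyroidism and hyperthyroidism among the drug-related events seen in at least 10% of patients in the earlier study of this combination, so the TSH interval has a clinical purpose.

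**Working it through.** The plan gives no computed figure to reproduce. The check is interval arithmetic.

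**Inputs**

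- Cycle length from Cycle 3 on: 28 days (Table 7.1-4 title).
- Shortest dosing interval from Cycle 3 on: 27 days (Section 6.5.1).
- Frequency in both cells: every 2 cycles (Table 7.1-4).
- Pregnancy note: at most 4 weeks, 4 × 7 = 28 days.
- TSH note: 6 weeks ± 1 week, 42 ± 7 = 35 to 49 days.

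**Interval implied by the cells**

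- On schedule: 2 × 28 = 56 days.
- At the shortest dosing: 2 × 27 = 54 days.
- Late doses only lengthen it.

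**Comparison over the 24 weeks (168 days) after Cycle 3 Day 1**

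| Row | Interval from cell | Limit from note | Excess, nominal (shortest) | Tests by cell | Tests by note |
|---|---|---|---|---|---|
| Pregnancy | 56 days | 28 days | 28 days (26) | 168/56 = 3 | 168/28 = 6 or more |
| TSH | 56 days | 49 days | 7 days (5) | 168/56 = 3 | 168/42 = 4 |

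The TSH count of 4 is at the nominal 6-week spacing. If every gap were stretched to 49 days, tests on days 49, 98 and 147 would satisfy the note with 3. In that case the cell is wrong on timing (56 against 49 days), not on count.

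**Can cell and note both be met?**

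- Pregnancy: yes. Testing every 28 days includes a test at every second Day 1. The note sets a minimum frequency, so testing more often than the cell says satisfies both.
- TSH, if the note means fixed 6-week due dates: yes, by adding tests at due dates that the cell's visits miss.
- TSH, if the note limits the gap between consecutive tests to 35–49 days: no. One gap of 56 days is too long, and two gaps need at least 2 × 35 = 70 days, more than 56.

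**Why Cycles 1 and 2 are not affected**

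Those cycles last 42 days. TSH on Day 1 gives exactly 6 weeks, and pregnancy tests on Days 1 and 22 are 21 days apart. With 28-day cycles, one cycle is 28 days and two are 56. No whole number of cycles falls within 35 to 49 days, so with dosing on schedule no Day 1 pattern can reproduce the TSH note.

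**The case against.** The best defence is that the notes already state the rule. The pregnancy note is a floor and says that it applies whatever the dosing schedule, so it overrides a cycle-based mark beside it. Essentially the same sentence stands in Tables 7.1-2, 7.1-3 and 7.1-4. For TSH, Table 7.1-2 applies the 6-week rule throughout. Harm needs a site to read the cell and ignore the note next to it. Even then, adverse events are assessed continuously, other laboratory tests are drawn every cycle, and contraception is required.

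Most of this stands, and it limits the weight of the point. A reader might infer that the pregnancy cell and its note cannot both be followed. The documents do not support that, because a site testing every 4 weeks meets both. A reader might also infer that the TSH cell and note are incompatible however they are read. That holds only if the note is a strict limit on the gap between tests, and the protocol does not say so.

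The defence does not make the cells correct. If the notes govern, the two-cycle qualifier understates what is required. The wording about the dosing schedule appears only in the pregnancy note, so it does not show which TSH entry was meant. Appendix 1 does not settle the matter, because it refers maintenance back to this table.

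**Conclusion.** The point holds as a minor inconsistency in an operative safety schedule. Followed alone, the pregnancy cell doubles the permitted interval (56 against 28 days) and halves the tests (3 against at least 6 in 24 weeks). The TSH cell exceeds the 49-day upper limit by 7 days, or 5 at the shortest dosing, and gives 3 tests against 4 at nominal spacing.

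The counts assume a participant who stays on maintenance for 24 weeks after Cycle 3 Day 1 with dosing on schedule. The practical effect also depends on how many women of childbearing potential enrol, which the documents do not give, and on how many sites schedule from the grid. Sites that follow the notes meet the stated rule. Neither test enters the definition of PFS or OS, the two-stage sample size, or the toxicity and futility stopping rules, so none of these changes.

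**What to change.** Delete the two-cycle qualifier from both cells of Table 7.1-4.

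- **Pregnancy test:** mark it every cycle for women of childbearing potential, with an extra test if the next dose falls more than 28 days after the last test. Cost: nothing beyond what the note already requires, apart from an occasional extra test when a dose slips.
- **TSH, option 1:** enter *See Note*, as this table already does for imaging and biomarkers, so that the 6-week rule governs. This adds no tests beyond the note, but some draws fall between visits. Counted from Cycle 3 Day 1, the due dates are days 42, 84, 126 and 168. Days 84 and 168 coincide with Day 1 visits, while days 42 and 126 are 14 days from the nearest one, outside the 7-day window.
- **TSH, option 2:** mark it every cycle and reword the note as a maximum interval. This costs 168/28 = 6 tests against 4, about 2 extra per participant per 24 weeks, at visits that already draw blood.

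Rewording the TSH note to about 8 weeks would also remove the mismatch. It would relax a rule that Table 7.1-2 sets for the whole study, so it needs a clinical reason and a matching change there.

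The edit is two table cells, plus one note if TSH moves to every cycle.
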